Study Protocol and Statistical Analysis Plan

Document Title: Chronic Lumbar Disc Herniation: A Randomized Single-Blind Study on the Comparative Efficacy of Peloid therapy Versus Hot pack Therapy

NCT Number: NCTXXXXXXX

Document Date: July 20, 2025

Study Protocol

Study Design

This study is a single-blinded, randomized controlled trial involving 60 individuals diagnosed with chronic lumbar disc herniation (LDH). Participants were randomly assigned into two groups: peloid therapy + TENS and hotpack therapy + TENS. Each group received treatment for 3 weeks (15 sessions).

Inclusion Criteria

Adults aged 18-50 with LDH symptoms for more than 3 months, confirmed by MRI, without physiotherapy in the last 6 months.

Exclusion Criteria

Severe neurological deficit, malignancy, osteoporosis, inflammatory diseases, systemic disorders, or contraindications for therapy were excluded.

Interventions

Peloid therapy was applied at 45°C for 30 minutes; hotpack therapy at 90°C for 20 minutes. Both followed by 20 minutes of conventional TENS.

Study Protocol and Statistical Analysis Plan

Outcome Measures

Primary outcomes include pain (VAS), disability (ODI), and functionality (BPFS). Secondary outcomes include quality of life (SF-36), ROM, and finger-floor distance. Assessments were performed pre- and post-treatment.

Statistical Analysis Plan

Sample size was determined using G*Power software based on an effect size of 0.759 from a prior study. A total of 42 participants were required to detect significant differences with 95% confidence and 5% alpha error.

SPSS 22.0 software was used. Descriptive statistics included mean, standard deviation, frequency, and percentage. Between-group differences were analyzed using independent samples t-tests and chi-square tests. Within-group comparisons were conducted using paired samples t-tests. A p-value < 0.05 was considered statistically significant.

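### Do the different temperatures and contact times in the two arms prevent a fair comparison of peloid with hot pack?

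*Combined protocol and SAP*

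**What the plan says.** The title describes "A Randomized Single-Blind Study on the Comparative Efficacy of Peloid therapy Versus Hot pack Therapy". Study Design gives the allocation: "Participants were randomly assigned into two groups: peloid therapy + TENS and hotpack therapy + TENS". It also gives both groups the same course, 15 sessions over three weeks.

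The Interventions section sets out the heat component in one sentence: "Peloid therapy was applied at 45°C for 30 minutes; hotpack therapy at 90°C for 20 minutes". The next sentence covers the shared component: "Both followed by 20 minutes of conventional TENS".

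The document does not say whether either temperature is that of the heating source, the pack or the skin surface. It gives no reason for the unequal times. It states no aim of separating the effect of the peloid material from that of heat, and it draws no conclusion about mechanism.

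**The concern.** Two features of the Interventions sentence catch the eye.

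The first is attribution. Three things change at once between the arms: the material, the temperature figure and the minutes of contact. If the peloid arm did better on VAS, ODI or BPFS, longer contact might be the reason. A reader who took the result as evidence for the peloid substance would be going beyond the data.

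The second is the basis of the temperatures. A single verb governs both figures, so read literally both are temperatures as applied to the patient. If one was taken at the source and the other at the point of contact, they are not on the same footing and the description of at least one arm is inexact. A reader then cannot tell how much heat the comparator arm received, and someone repeating the treatment from this text could misread it, which would bear on patient safety.

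At stake would be the meaning of the main between-group comparison and the reproducibility of the treatments.

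**Working it through.** **Inputs**

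| Item | Peloid arm | Hot pack arm | Source |
|---|---|---|---|
| Temperature figure | 45°C | 90°C | Interventions |
| Contact time per session | 30 min | 20 min | Interventions |
| TENS per session | 20 min | 20 min | Interventions |
| Sessions | 15 | 15 | Study Design |

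The plan gives no figure of its own on this point to reproduce. Its one calculated number, a required sample size of 42, does not enter.

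**Step 1: size of the differences** (total = sessions × minutes per session)

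- Peloid contact: 15 × 30 = 450 min.
- Hot pack contact: 15 × 20 = 300 min.
- Difference: 450 − 300 = 150 min. Ratio: 450 / 300 = 1.5.
- Temperature figures: 90 − 45 = 45°C apart.
- TENS: 15 × 20 = 300 min in each arm, difference 0.

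The longer contact is in the peloid arm and the higher temperature figure is in the hot pack arm. Without a common measurement point, the document does not show which arm received more heat, so even the direction of any imbalance is unknown.

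**Step 2: what two randomised arms can estimate**

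Write the contrast as τ = mean outcome under the peloid regimen − mean outcome under the hot pack regimen. Two arms supply one between-arm contrast. Material, temperature and time are three factors that each take one value per arm, so they coincide completely with the arm label. One contrast cannot be split into three effects by the t-tests and chi-square tests in the Statistical Analysis Plan, or by any other analysis of these two arms. To that extent the concern is correct.

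Randomisation does, however, estimate τ itself, because each regimen is assigned as a unit.

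**Step 3: which quantity the document asks for**

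The title compares "Comparative Efficacy of Peloid therapy Versus Hot pack Therapy", and Study Design randomises each therapy with TENS. Both describe whole treatments. TENS and session count are held equal, so the heat treatment, with its own settings, is the only planned difference. The quantity named in the document is τ, and τ is estimable. The material-only effect is not estimable, but the document does not claim to estimate it.

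**Step 4: do the temperatures contradict each other?**

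Side by side, "Peloid therapy was applied at 45°C for 30 minutes" and "hotpack therapy at 90°C for 20 minutes" describe different modalities. Each modality has one temperature and one duration, and no other place in the document gives a second value for either. Nothing conflicts. The measurement point is unstated, which is an ambiguity.

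**Step 5: what would change if the details were supplied**

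Naming the measurement points and the reason for the unequal times would leave the arms, the allocation, the outcomes, the sample size and the tests as they are.

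**The case for a change.** The best argument for acting is that clarification costs almost nothing and the gap touches the main contrast. The title names the arms by modality alone, so a reader of a positive result may credit the substance. A limit on interpretation is most convincing when stated in advance. And a text that leaves open what heat the comparator received does not describe the intervention well enough to be repeated.

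Much of this stands as advice on reporting. The eventual paper should describe its result as one regimen against another, say where each temperature was measured, and give the reason for the different times. A competent author would do this without being told by the plan.

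It falls short of a defect in the plan for three reasons. There is no stated conclusion to narrow, because the document makes no claim about the material. The document is written in the past tense, so treatment appears to be finished and no treatment setting can now be altered. The safety worry depends on a later user taking an ambiguous sentence literally, and the document mentions no further use and gives no contact-temperature limit by which to judge the figure. Whether to match contact time across modalities or give each its own regimen is a choice of research question, and both designs are legitimate.

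**Conclusion.** No change to the plan follows. The arms do differ in more than material: 450 against 300 minutes of heat contact over the course (ratio 1.5), and temperature figures 45°C apart. A between-arm difference therefore supports a statement about the two regimens as delivered and cannot be carried over to the peloid material as such. That is the comparison the title and Study Design describe, and randomisation supports it.

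The remaining gap is missing descriptive detail: the point at which each temperature was measured and the reason for the unequal times. It alters no design element, analysis or stated conclusion.

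This rests on reading the title and arm definitions as a comparison of whole therapies, and on the past tense meaning that treatment is complete. If a report claimed a peloid-specific effect, this design could not support it. The effect on VAS, ODI or BPFS cannot be quantified from the document, and no view is taken here on which temperature or duration is appropriate.

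### Three unranked primary outcomes are each tested at 0.05 with no success rule or multiplicity control; if any one can carry the claim, the false-positive chance is up to about 14%.

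*Combined protocol and SAP*

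**What the plan says.** The combined document is short, and four statements in it bear on this point.

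- Outcome Measures: "Primary outcomes include pain (VAS), disability (ODI), and functionality (BPFS"). Assessment is before and after treatment. The three outcomes are given no order and no lead outcome is named.
- Statistical Analysis Plan, between-group tests: "Between-group differences were analyzed using independent samples t-tests and chi-square tests".
- Statistical Analysis Plan, threshold: "A p-value < 0.05 was considered statistically significant".
- Statistical Analysis Plan, sample size: "Sample size was determined using G*Power software based on an effect size of 0.759 from a prior study", followed by "A total of 42 participants were required to detect significant differences with 95% confidence and 5% alpha error". The outcome that the effect size belongs to is not given, so this sentence does not single out a main outcome either.

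Study Design describes a "single-blinded, randomized controlled trial involving 60 individuals" and gives no allocation ratio. The document contains no hierarchy, no split of alpha, no adjustment, and no definition of a positive trial.

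**The concern.** Three primary tests, each at 0.05, give three chances of a false-positive primary finding. Whether that matters depends on how the three results combine into a conclusion, and the plan does not say. At least three readings fit the text:

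1. A difference on any one outcome is a primary finding.
2. All three must show a difference.
3. Each outcome is a separate question and no overall claim is made.

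These readings have very different error rates and power. The title promises a single conclusion on comparative efficacy. With no rule on record, that conclusion can be settled after the p-values are known. A trial with, say, a significant VAS result and non-significant ODI and BPFS results would succeed under the first reading and fail under the second.

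**Working it through.** **Inputs from the document.** Three primary outcomes; threshold 0.05 per test; independent-samples t-tests; one post-treatment assessment; 60 patients in two groups; effect size 0.759; stated requirement 42.

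**Assumptions not in the document.** Two-sided tests (sidedness is not stated); equal allocation, so 60/2 = 30 per arm; equal pairwise correlation r among the three outcomes, varied from 0 to 0.9; for power only, a true standardised difference of 0.759 on all three outcomes.

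**The plan's own figure.** The plan gives no error rate for the set of primary tests, so there is none to reproduce. Its sample size of 42 cannot be checked either, because power and sidedness are not stated. The false-positive figures below hardly depend on sample size.

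**Step 1: any one outcome counts, independent tests, no true difference.**
P(at least one p < 0.05) = 1 − (1 − 0.05)³ = 1 − 0.857375 = 0.1426.
The bound that holds under any dependence is 3 × 0.05 = 0.15.

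**Step 2: allow for correlation.** Three equicorrelated two-sided t-tests were simulated with 30 per arm, no true difference and 200,000 replicates:

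| r | Any one, either direction | Any one, favouring peloid | All three | Any one after Holm |
|---|---|---|---|---|
| 0 | 14.3% | 7.3% | 0.01% | 4.9% |
| 0.5 | 12.5% | 6.3% | 0.3% | 4.5% |
| 0.7 | 11.0% | 5.5% | 0.9% | 4.0% |
| 0.8 | 9.9% | 4.9% | 1.3% | 3.5% |
| 0.9 | 8.3% | 4.2% | 2.2% | 3.0% |

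The nominal rate is 5% in either direction and 2.5% in favour of peloid alone. A separate normal-theory simulation (2,000,000 draws) gave any-one rates of 14.3%, 12.5%, 11.0%, 9.8% and 8.4%, so the results agree within simulation error. With 21 per arm (42/2) the any-one rate is 14.1% at r = 0, 12.6% at 0.5 and 8.4% at 0.9.

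**Step 3: the all-three rule when some outcomes differ.** The all-three column assumes no difference anywhere. If two outcomes truly differ by 0.759 and the third does not, the rule errs about 3% of the time at r = 0.5–0.7 with 30 per arm. Its ceiling is 5%.

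**Step 4: power under each rule** (true difference 0.759 on all three; r = 0.5 to 0.7; 30 per arm).

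- Unadjusted, per outcome: 82%.
- Unadjusted, at least one: 96% to 93%.
- All three: 65% to 69%.
- Holm, average per outcome: 76.2% to 75.5%.
- Holm, at least one: 89% to 85%.

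With 21 per arm, per-outcome power falls from 67% unadjusted to about 57% with Holm.

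**The case against.** The strongest reply is that the plan never claims a 5% error rate for the set of primary tests. The phrase "with 95% confidence and 5% alpha error" sits in a sample-size sentence built on a single effect size, and 0.05 is a per-test threshold. If the three outcomes are reported as three separate findings, each keeps its own 5%. This is a fair description of the text, but it confirms the gap: the separate-findings reading is defensible only if it is stated and no overall efficacy claim follows, and the plan does neither.

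Second, 14% is the extreme case. Pain, disability and function in the same patients are probably positively correlated, which lowers the figure, and errors favouring peloid alone are about half as frequent. This stands as a point about size, and a range of about 8–14% is the fair summary. It does not remove the problem: at r = 0.9 the any-one rate is still 8.3% against 5%, and 4.2% against 2.5% for peloid. If the tests were in fact one-sided at 0.05, the rate favouring peloid would be about 14% at r = 0, 12% at 0.5 and 8% at 0.9.

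Third, the 0.3% for the all-three rule holds only when no outcome differs. That is correct, and it is why the 3% figure and the 5% ceiling are given above. The gap between readings narrows but remains.

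Fourth, the plan does not say whether the t-tests compare post-treatment scores or changes from baseline, so two sets of p-values are possible. This is a separate gap. It does not make Holm invalid, but it has to be closed for the rule to be unambiguous.

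Last, the past tense ("SPSS 22.0 software was used") suggests that the analysis is done, in which case a rule added now cannot restore prespecification. That is true, and the rule must then be labelled accordingly.

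**Conclusion.** The concern holds. The plan leaves the meaning of a positive trial undefined. If any one of the three primary outcomes can support the claim, the chance of a false primary finding is about 8% to 14%, and it exceeds 5% at every correlation examined. The figure rests on two-sided tests and on correlations that the document does not give; arm size hardly affects it. It is conditional on the any-one reading: had the plan required all three, the error could not exceed 5%. The defect bears on the trial's main conclusion and can be corrected with a few sentences, so it must be fixed.

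**What to change.** Add one decision rule to the Statistical Analysis Plan. Apply Holm to the three primary between-group p-values: compare the smallest with 0.05/3 = 0.0167, the next with 0.05/2 = 0.025 and the largest with 0.05, stopping at the first failure. Claim a primary effect only on outcomes that pass. In the same paragraph, state that the tests are two-sided if they are, and which comparison (post-treatment score or change from baseline) supplies each p-value.

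State when the rule was adopted. If outcome data had already been analysed, report the Holm results as post hoc.

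A single named primary outcome, a fixed testing order or an all-three requirement would also control the error if chosen before the data were seen. Holm is preferred here because it needs no ranking, which is hard to choose credibly after the results are known.

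The cost is a short addition and a timing statement. No new data are needed, and Holm can be applied to existing p-values. Under the power assumptions above, average power per outcome falls by 6 to 7 percentage points at 30 per arm and by about 10 points if only 42 patients are analysed (67% to about 57%).

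### The stated requirement of 42 does not follow from an effect size of 0.759 for the between-group t-test at any conventional power, and the plan omits the inputs needed to trace it

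*Combined protocol and SAP*

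**What the plan says.** The title describes "A Randomized Single-Blind Study on the Comparative Efficacy of Peloid therapy Versus Hot pack Therapy". Under Study Design the trial is a "randomized controlled trial involving 60 individuals diagnosed with chronic lumbar disc herniation (LDH"), and "Participants were randomly assigned into two groups: peloid therapy + TENS and hotpack therapy + TENS". The allocation ratio is not given. Outcome Measures lists three primary outcomes: VAS pain, ODI disability and BPFS functionality.

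The Statistical Analysis Plan covers sample size in two sentences: "Sample size was determined using G*Power software based on an effect size of 0.759 from a prior study" and "A total of 42 participants were required to detect significant differences with 95% confidence and 5% alpha error".

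For the comparison of the two arms it says: "Between-group differences were analyzed using independent samples t-tests and chi-square tests". For change inside each arm it adds: "Within-group comparisons were conducted using paired samples t-tests". The threshold for both is then set: "A p-value < 0.05 was considered statistically significant".

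It does not say which test was sized, what kind of effect size 0.759 is, which primary outcome it belongs to, whether the test was one- or two-sided, what power was targeted, or how 42 relates to 60.

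**The concern.** The question in the title is between groups, and the t-test named for between-group differences is the independent-samples t-test. A reader will therefore take 42 as the number needed to compare peloid with hot pack. The exact independent-samples t-test with 0.759 does not return 42 at 80%, 85%, 90% or 95% power, one- or two-sided.

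The wording does not settle the power either. A 95% confidence level is one minus a 5% alpha, so on its plain meaning the sentence gives the same quantity twice and no power. It could be a slip for 95% power, but then the independent-samples test needs far more than 42.

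These two sentences are the document's only justification of the trial's size. As they stand, a reader cannot tell whether the trial was sized for the comparison in its title or for change within a group.

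**Working it through.** **Inputs from the Statistical Analysis Plan and Study Design.** Effect size 0.759; alpha 0.05; stated total 42; trial size 60; independent-samples t-test between groups; paired t-test within groups.

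**Assumptions, not in the document.** 1:1 allocation (21 per group for 42, 30 per group for 60); one outcome; 0.759 is a standardised between-group difference in steps 1 to 4 and a standardised paired difference in step 5; conventional target powers are 80%, 85%, 90% and 95%; both one- and two-sided tests are tried.

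**Step 1. Power of the independent-samples t-test with 42.** With n per group, df = 2n − 2 and noncentrality δ = d × √(n/2). Power is the probability that a noncentral t exceeds the critical value (in either direction if two-sided).

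For n = 21: df = 40, δ = 0.759 × √10.5 = 2.459.
- Two-sided, critical value 2.021: power 67.0%.
- One-sided, critical value 1.684: power 78.0%.

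With n = 20 the figures are 64.8% and 76.2%. So 42 is the smallest equal-group total only for a target power above 64.8% and up to 67.0% (two-sided), or above 76.2% and up to 78.0% (one-sided).

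**Step 2. Total needed at conventional power.** Smallest n per group reaching the target, doubled:

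| Target power | Two-sided total | One-sided total |
|---|---|---|
| 80% | 58 | 46 |
| 85% | 66 | 52 |
| 90% | 76 | 62 |
| 95% | 94 | 78 |

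If the 95% in the text was meant as power, the last row applies, and the gap from 42 is 52 participants two-sided (94 − 42) or 36 one-sided (78 − 42).

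**Step 3. The nearest between-group route.** The normal approximation with one-sided 5% alpha and 80% power is n = 2(1.645 + 0.842)²/0.759² = 21.5, rounded up to 22 per group, 44 in total. The exact t-test has 79.7% power at 22 per group and 81.3% at 23, so it gives 46. Neither is 42.

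**Step 4. The 60 in the design.** For n = 30: df = 58, δ = 0.759 × √15 = 2.940, critical value 2.002, two-sided power 82.4%. At 29 per group power is 81.1%; at 28 it is 79.6%.

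If 0.759 is not a between-group difference, the document gives no between-group effect. Over an assumed range of 0.3, 0.5 and 0.759, 30 per group has 21%, 48% and 82% power two-sided. Power of 80% corresponds to a standardised difference of about 0.74.

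**Step 5. Other tests that might have produced 42.** For a paired t-test with n pairs, df = n − 1 and δ = 0.759 × √n.
- n = 21: δ = 3.478; power 91.1% two-sided, 95.7% one-sided.
- n = 20: δ = 3.394; power 89.6% two-sided, 94.8% one-sided.

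So 21 is the minimum for 90% two-sided or 95% one-sided, and 2 × 21 = 42. The one-sided version would also fit a reading of the 95% as power.

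At 80%, 90% and 95% power, treating 0.759 as Cohen's f with two groups gives 16, 22 and 26 in total, and as chi-square w with 1 df gives 14, 19 and 23. None is 42.

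**The case against.** The strongest reply is that this is incomplete reporting and not a demonstrated error. With the test, effect-size type, outcome, sidedness and power all unstated, 42 cannot be shown to be wrong, and one route returns it exactly. That stands. A reader might infer that the calculation was botched; the documents do not support that, because under a paired test 42 would be a correct output.

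The opposite inference, that 42 did come from a paired test, is not supported either. The match emerged after several tests, powers and both sidedness options had been tried, with a doubling step added. A hit from such a search is weak evidence of origin.

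It can also be said that one-sided 80% power comes close, at 44 by the normal approximation. That route needs an unstated one-sided test, an unstated power and a z formula in place of the t-test, and it still does not give 42.

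Finally, the trial has 60 participants, enrolling more than a stated minimum is not a contradiction, and the plan is written in the past tense, so no recruitment decision appears to turn on 42. This limits the practical consequence. It does not repair the justification: 42 is still presented as what was required, and no independent-samples calculation at conventional power supports it for the title comparison.

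**Conclusion.** The point holds as a defect in the stated justification. Given a between-group standardised difference of 0.759, 1:1 allocation and 5% alpha, 42 participants give 67% power two-sided or 78% one-sided. At 80% power the shortfall is 16 participants two-sided (58 − 42) or 4 one-sided (46 − 42). If 0.759 is instead a pre-post effect, it says nothing about power between groups. On neither reading does 42 support peloid versus hot pack at 80% power.

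A reader might go further and infer that the trial itself is underpowered. The documents do not show this: on the between-group reading, 60 exceeds the 58 needed and gives 82% two-sided power for one outcome. The margin is thin, since 28 analysed per group falls just below 80%, and 60 does not reach the 76 needed for 90%.

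The conditional figures are firm. The origin of 42 is unknown. This should be corrected, as a matter of wording.

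**What to change.** Recover the G*Power inputs and state them: outcome, type of effect size, test, sidedness and target power. State how 60 relates to 42. Then choose according to the calculation that was actually run:

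- **Independent-samples test, with 0.759 as a between-group difference.** Replace the statement that 42 were required with: *Recalculation, not the original basis: 58 in total are needed for 80% power (two-sided alpha 0.05); 30 per group gives 82% for a standardised between-group difference of 0.759 on [named outcome].*
- **Paired test.** Say that 42 refers to the within-group test and that the trial was not sized for the between-group comparison.
- **Another test or effect-size type, or inputs that cannot be recovered.** Say so, and do not present 42 as the requirement for the between-group comparison.

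Unless the first case applies, add that 30 per group has 80% power for a standardised between-group difference of about 0.74 (two-sided alpha 0.05). If the analysed groups were not 30 and 30, recompute with the actual sizes.

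No extra participants and no change to any test are needed. The cost is a less favourable sample-size statement: 82% power for one outcome, or an admission that the trial was not sized for its between-group comparison or that the basis of 42 is unknown.

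### The between-group t-test does not name the score it compares, and baseline-adjusted ANCOVA on data already collected would be more precise than either reading.

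*Combined protocol and SAP*

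**What the plan says.** Under Outcome Measures, three primary outcomes are listed (VAS, ODI and BPFS), with SF-36, ROM and finger-floor distance as secondary. On timing: "Assessments were performed pre- and post-treatment". Each outcome therefore has a baseline value and one follow-up value.

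Under Statistical Analysis Plan, the between-group method is: "Between-group differences were analyzed using independent samples t-tests and chi-square tests". The plan adds: "Within-group comparisons were conducted using paired samples t-tests". The threshold is: "A p-value < 0.05 was considered statistically significant".

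Nothing else bears on the point. The plan does not say which score enters the between-group t-test, and it names no baseline covariate or adjusted model. The paired tests look at change inside each arm; they do not estimate the difference between arms.

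The sample-size statement gives a standardised effect without its outcome or scale: "Sample size was determined using G*Power software based on an effect size of 0.759 from a prior study".

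**The concern.** Two different analyses fit the plan as written: a t-test on post-treatment values and a t-test on pre-post changes. They have different standard errors and different p-values. Chance imbalance at baseline also moves them in opposite directions. A reader cannot tell which one the plan means, and the choice recurs for each of three primary outcomes and every secondary score.

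Neither version makes the best use of the baseline. The post-value test ignores it. The change score subtracts it in full, which over-corrects when the pre-post correlation is below 1 and the two SDs are equal. ANCOVA estimates the correction from the data. At stake are the width of the confidence intervals for the primary comparisons and protection against selecting the more favourable of two results.

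**Working it through.** **Inputs from the documents.** 60 randomised to two groups; significance threshold 0.05; effect size 0.759; stated requirement of 42 participants.

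**Assumptions not in the documents.** 1:1 allocation (n = 30 per arm), two-sided test, equal pre and post SDs, no dropout, and pre-post correlation r = 0.3, 0.5 or 0.7.

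**1. The plan's own figure.** The 42 cannot be derived from what is stated, because neither power nor sidedness is given. For an independent t-test, two-sided 5%, d = 0.759, noncentral t gives a total of 58 for 80% power and 76 for 90%; 42 gives 67.0%. A paired t-test needs 21 pairs for two-sided 90% power, and 2 × 21 = 42, but the plan does not say that this was the calculation. The comparison below uses the 60 randomised and does not depend on the 42.

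**2. Variance of the estimated difference**, relative to the post-value t-test (large sample):
- post-value t-test: 1
- change-score t-test: 2(1 − r)
- ANCOVA: 1 − r²

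Relative to the change score, ANCOVA is (1 − r²) / [2(1 − r)] = (1 + r)/2.

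| r | ANCOVA / post-value | ANCOVA / change |
|---|---|---|
| 0.3 | 0.91 | 0.65 |
| 0.5 | 0.75 | 0.75 |
| 0.7 | 0.51 | 0.85 |

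**3. Cost of estimating the slope.** At N = 60 the ANCOVA variance is multiplied on average by 57/56 = 1.018.
- ANCOVA beats the post-value test when (1 − r²) × 1.018 < 1, that is, r above √(1 − 56/57) = 0.13.
- It beats the change score when (1 + r)/2 × 57/56 < 1, that is, r below 2 × 56/57 − 1 = 0.965.

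**4. 95% CI half-width in post-treatment SDs.**
- Post-value: 2.00 × √(2/30) = 0.52.
- Change: multiply by √(2(1 − r)).
- ANCOVA: multiply by √((1 − r²) × 1.018), with 57 degrees of freedom.

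| r | ANCOVA | Post-value | Change |
|---|---|---|---|
| 0.3 | 0.50 | 0.52 | 0.61 |
| 0.5 | 0.45 | 0.52 | 0.52 |
| 0.7 | 0.37 | 0.52 | 0.40 |

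**5. Power (noncentral t, two-sided 5%).** The scale of 0.759 is unstated, so both between-group readings are shown.

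| r | Scale of 0.759 | ANCOVA | Post-value | Change |
|---|---|---|---|---|
| 0.3 | post-value SD | 85% | 82% | 69% |
| 0.5 | post-value SD | 91% | 82% | 82% |
| 0.7 | post-value SD | 98% | 82% | 96% |
| 0.3 | change SD | 94% | 93% | 82% |
| 0.5 | change SD | 91% | 82% | 82% |
| 0.7 | change SD | 87% | 61% | 82% |

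ANCOVA is highest in every row. Which t-test comes second depends on r.

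**6. Chance baseline imbalance.** The SD of the baseline difference is √(2/30) = 0.258. The probability that it exceeds 0.25 SD in either direction is 2 × [1 − Φ(0.25/0.258)] = 0.33. At r = 0.5, an imbalance of 0.25 SD shifts the post-value difference by 0.5 × 0.25 = +0.125 SD and the change-score difference by (0.5 − 1) × 0.25 = −0.125 SD.

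**7. Simulation of the open choice** (bivariate normal, 40,000 or more trials per setting).
- Each t-test alone, and ANCOVA, has a type I error of about 5%.
- With a true difference of 0.759 post-value SD, the two t-tests disagree at p < 0.05 in about 26, 21 and 18% of trials at r = 0.3, 0.5 and 0.7.
- With no true difference they disagree in about 8 to 9%, and at least one is significant in about 9%.

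**The case against.** The strongest reply is that nothing here is invalid. Either t-test, fixed in advance, is unbiased with 5% type I error. Naming the score would close the ambiguity, and ANCOVA is then only a matter of efficiency. This stands as a limit on the claim, but not as a reason to forgo a gain that needs no new data.

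Second, the document is in the past tense (for example, "SPSS 22.0 software was used"), so the analysis may already be done and the planning gain no longer available. That is a real possibility, and the remedy is conditional for that reason.

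Third, the gain is an average and rests on an r that the documents do not give. Between r = 0.3 and 0.7 the variance saving against the post-value test runs from 9% to 49%. In single trials the ANCOVA interval can be the wider one: in simulation, about 18% of the time against the post-value test at r = 0.3, and about 6% against the change score at r = 0.7. The direction is firm over the realistic range; the size is not.

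Fourth, 0.759 may be a within-group effect, since 42 matches a paired calculation. If so, neither set of power figures describes this trial. The variance ratios and interval widths do not use 0.759 and are unaffected.

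Last, the 9% error rate requires someone to run both tests and report the favourable one. Nothing in the document suggests that this happened. It measures what the wording permits, not an expected error rate.

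**Conclusion.** The concern holds. The between-group score is unspecified, and no baseline adjustment is planned although every outcome has a baseline. This is an improvement that should be made, not the repair of an invalid test. For r between 0.3 and 0.7, ANCOVA lowers the variance by 9 to 49% against the post-value t-test and by 15 to 35% against the change-score t-test, before a slope-estimation cost of about 1.8%. These figures assume 30 per arm, equal SDs at both times and no dropout. ANCOVA loses its advantage only outside r of about 0.13 to 0.965. Confidence is high on the ambiguity and on the direction of the gain; its size depends on r.

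**What to change.** **If outcomes have not yet been compared by group:** for VAS, ODI, BPFS, each SF-36 score, ROM and finger-floor distance, state that the between-group analysis is an ANCOVA of the post-treatment value on group and the baseline value of the same measure. Report the adjusted mean difference with its 95% CI and two-sided p-value. Keep the t-test as a sensitivity analysis and name the score it compares.

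**If they have been compared:** keep the stated t-test, say whether it used post-treatment values or changes, and report the ANCOVA beside it as a dated, disclosed post hoc analysis.

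**Cost:** a few lines in the SAP and one general linear model per outcome in the software already named; no new data. The statistical cost is one degree of freedom and the slope estimate. If r were 0, power would be 81.7% instead of 82.4% (0.759 in post-value SDs, 30 per arm). In the second case, the cost also includes declaring a post hoc amendment.
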